11.0 Data and Safety Monitoring

- We have developed a formal data safety and monitoring plan to ensure the ongoing safety of participants (as well as the integrity of the study). The plan involves weekly meetings that will be used to communicate any concerns or issues with safety, confidentiality, or progress.
- Suicidal Ideation: The PI is a clinician and has extensive experience in the assessment of acutely depressed and anxious patient volunteers at screening and in the context of lab assessments. The PI routinely evaluates for suicidal ideation, behavior and risk, and will consult with and closely oversee the clinical monitoring and suicide assessment during the study. If suicidality is endorsed by a participant at any point during the assessment or experimental portion of the study, appropriate steps will be taken. Specifically, the PI or trained study staff member will a) obtain a more detailed assessment of intent, plan and method, including using the gold-standard, empirically-validated Columbia Suicide Severity Rating Scale (CSSRS)⁷⁰; b) discuss the situation with the participant, the participant’s emergency contact, and/or members of the mentorship team as warranted; c) consult with the PI and/or CO-Is; and d) make an appropriate treatment referral for the participant. If the PI believes that the participant is in imminent danger, they will call 911 or will walk the participant over to the emergency room at the Ohio State University hospital, only 1 block away.

- Once enrolled, participants who show deterioration between assessment and the lab tasks (e.g., increased anxiety, depression, mania, psychosis, or suicidality) may be removed from the study and referred to our outpatient psychiatry clinic or emergency psychiatric evaluation, if necessary. Participants who are deemed to be at high risk during either the assessment or experimental session may need to be psychiatrically hospitalized. If the CSSRS indicates suicidal thinking or if suicidal behavior is present, or if there is any concern about current suicide risk, the PI will evaluate suicide risk and decide what level of care is sufficient. The PI will then facilitate follow-up visit, Emergency Room/emergency department visit or inpatient admission if necessary.
- Weekly meetings of the research staff of this study will be conducted that will include review of accrual, consenting procedures, protocol adherence, adverse events, and quality control of all data obtained from the study in the previous week. All changes in protocol design will be reviewed by the IRB before such changes in protocol design take place.
- All AEs occurring during the course of the study will be reported to the PI. Serious adverse events (SAEs) will be reported by the PI to the IRB within 5 business days of the PI (or her team's) knowledge of the SAE. Moderate adverse events (AEs) that are unexpected and indicate that the research is associated with a greater risk of harm to participants or others than previously known will be reported to the IRB within 15 business days of the PI's (or her team's) knowledge of the event. All mild AEs and moderate AEs that are expected or are not associated with a greater risk of harm to participants or others than previously known will be reported to the IRB at the scheduled Continuing Review.

12.0 Statistical Considerations

13.0 Aim 1. Does a single dose of SUV decrease reactivity to U-threat? Hypothesis

1: Relative to PBO, SUV will acutely dampen startle reactivity to U-threat, but not P-threat. We will conduct a multilevel mixed model with startle magnitude as the dependent variable. Startle to U-threat and P-threat will be included as a within-subjects factor, to test for specific changes in U-threat. Time (baseline vs. acute challenge) and treatment arm (SUV vs. PBO) will be included as within-subjects and between-subjects factors, respectively, and we expect a time x treatment arm x task condition interaction on startle. Models will include a random effect for participant.

14.0 Aim 2. Does daily use of SUV decrease reactivity to U-threat? Hypothesis 2a:

4-weeks of SUV will result in greater reductions in reactivity to U-threat compared with PBO, and these changes will be specific to U-threat. Hypothesis 2b: SUV-related change in U-threat reactivity will be greatest amongst those with higher baseline U-threat reactivity. Exploratory Analysis: SUV will similarly result in decreases in aINS and dACC reactivity and connectivity during U-threat relative to PBO, and brain change will correlate with startle change. For H2a, we will conduct a multilevel mixed model that is nearly identical to the model described for H1. However, the time variable will be modeled as baseline vs. post-treatment. For H2b,

we will include baseline startle to U-threat as a predictor in our model and test for a baseline startle by treatment arm interaction. Lastly, for our exploratory fMRI analyses, we will first extract activation and functional connectivity parameter estimates from anatomical aINS and dACC during U-threat (and P-threat) > No-threat contrast maps. fMRI variables will be tested as dependent variables in the model used for H2a. Magnitude of brain change will be directly correlated with magnitude of startle change.

15.0 Aim 3. Does daily use of SUV change alcohol behavior, and is this change linked to brain-behavior U-threat change? Hypothesis 3a: Daily SUV will result in greater reductions in PHDD and DPDD compared with PBO. **Hypothesis 3b:** SUV-related changes in PHDD and DPDD will be greatest in those with higher U-threat reactivity. **Hypothesis 3c:** In all subjects, changes in brain-behavioral U-threat reactivity will correlate with changes in drinking behavior. For H3a, linear mixed models will be used to assess the impact of treatment arm (SUV vs. PBO) on changes in drinking behavior over the 4-week follow-up period (daily reports). If the assumptions of linear models are violated due to skewed residual errors, we will explore the use of Poisson and negative binomial generalized linear mixed models to model drinking behavior. For H3b, baseline startle potentiation to U-threat (and in secondary models, aINS, dACC, and BNST parameter estimates) will be entered as a covariate/predictor and we will test for a baseline startle to U-threat by treatment arm interaction on drinking behavior outcomes. Lastly, the hypothesis for H3c will be tested using a linear mixed model that includes magnitude of U-threat and P-threat reactivity (startle and brain, separate models), time, and treatment arm as predictors and PHDD and DPDD as the outcomes. We expect a startle by time interaction such that regardless of treatment arm, a change in U-threat reactivity will correspond to a change in drinking behavior.

Sample Size. Our key hypothesis testing involves treatment arm by session interactions on startle eyeblink potentiation. Assuming a medium to large effect size, which is supported by our preliminary data, a sample size of 40 individuals per treatment group would conservatively yield 91% power (a total sample size of 80 individuals). To account for potential screen-fails, participants requesting to drop out of the study, and the PI withdrawing participants due to meeting termination criteria, approval for 120 participants is requested.

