1.0 PROJECT SUMMARY/ABSTRACT

Alcohol use disorder (AUD) affects millions and is one of the leading causes of preventable death worldwide. In the US, pharmacotherapy for AUD is under-utilized; related to the fact that there are only three FDA-approved drugs to treat patients with AUD. These medications work well for some but have small to moderate effect sizes on drinking outcomes. The development of more efficacious pharmacotherapies for AUD is a top public health priority. A recent emphasis in psychiatric medication development is the use of reliable human laboratory measures of AUD dysfunction to test promising compounds to directly inform and power large-scale mechanistic clinical trials. PI [name] and Co-I [name] have developed an assay of stress reactivity that is robustly related to drinking behavior and AUD. This assay reflects a negative reinforcement model of AUD and is reliably captured in the lab using complimentary objective psychophysiological (i.e., startle eyeblink potentiation) and functional neuroimaging measures. Using this model, we have uncovered that suvorexant (SUV) – a dual receptor antagonist of the orexin system, FDA-approved for insomnia – acutely modifies our AUD target in healthy adults, while sparing changes in other markers of stress reactivity. Compelling animal and human evidence together suggest that the orexin system is critically involved in stress-related alcohol use. The overarching goal of this study is to systematically advance this line of work to uncover if, how, and for whom orexin antagonism modifies brain-behavior stress targets of AUD to inform and power future large scale clinical trials. The study is a targeted double-blind, between-subjects, randomized clinical trial design with repeat lab assessment. A total of eighty subjects with AUD will complete our psychophysiological stress paradigm at baseline. They will return to the lab days later to repeat the protocol following administration of a single dose of either 10mg SUV or placebo (40 subjects/arm). Participants are then instructed to take daily 10mg capsules of SUV or placebo for the next 4-weeks before returning for a post-treatment lab assessment. Daily reports of medication adherence, side-effects, sleep, alcohol use, and mood will be collected via smartphones.

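### H1 and H2a enter baseline startle as an outcome level rather than adjusting for it, which is valid but gives away precision that costs nothing to recover

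*Combined protocol and SAP*

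**What the plan says.** Section 12.0 (Statistical Considerations) describes H1 as follows: "We will conduct a multilevel mixed model with startle magnitude as the dependent variable". U-threat versus P-threat is a within-subject factor, and the baseline visit enters through the time factor: "Time (baseline vs. acute challenge) and treatment arm (SUV vs. PBO) will be included as within-subjects and between-subjects factors, respectively". The effect of interest is stated as "we expect a time x treatment arm x task condition interaction on startle". The only covariance term is given by "Models will include a random effect for participant".

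H2a follows the same pattern: "For H2a, we will conduct a multilevel mixed model that is nearly identical to the model described for H1", except that "the time variable will be modeled as baseline vs. post-treatment".

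Baseline startle is a predictor only in the moderator analyses. For H2b, "we will include baseline startle to U-threat as a predictor in our model and test for a baseline startle by treatment arm interaction"; H3b does the same for drinking outcomes. No section makes baseline a covariate in the H1 or H2a treatment comparison, and none constrains baseline means to be equal across arms.

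The baseline data will exist. According to section 1.0, "A total of eighty subjects with AUD will complete our psychophysiological stress paradigm at baseline", before the first dose.

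**The concern.** In a factorial model with arm, time and their interaction, the arms have freely estimated baseline means. The arm-by-time term then subtracts the observed baseline difference in full. Because treatment is randomised and the baseline visit comes before dosing under blinding, that difference is expected to be zero. Subtracting all of it adds the noise of the baseline visit to the comparison. Adjustment subtracts only the part that predicts the follow-up score.

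At stake is precision in the comparison that the sample-size paragraph calls the key hypothesis test. The 91% power there rests on an effect described only as between medium and large. Section 10.0 adds a Bonferroni correction, which lowers power further. The summary also says the results will be used to power a larger trial, so narrower intervals have a second use.

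**Working it through.** **Inputs from the documents.** 40 per arm, 1:1 allocation, 91% power for arm by session (section 12.0, Sample Size). **Not given, so assumed:** two-sided alpha 0.05; correlation r between baseline and follow-up, 0.3 to 0.9; equal variances at the two visits.

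**1. The plan's own figure.** With a normal approximation, 91% power needs a noncentrality of 1.960 + 1.341 = 3.301. At 40 per arm, d = 3.301 / sqrt(40/2) = 0.738 in units of the SD of the change score (0.747 with the t distribution). At d = 0.5 power is 60.9%, and at d = 0.8 it is 94.7%. So 91% is compatible with the verbal effect size. It cannot be reproduced, because no numerical effect, alpha, sidedness or correlation is stated.

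**2. What the planned terms estimate.** A fit to one simulated complete data set (40 per arm) gave an arm-by-time estimate of -0.1278 with SE 0.1956 from a random-intercept model of U alone, and the same two values from the difference in mean change. The three-way estimate was 0.1983, equal in size to the arm difference in the change of U minus P.

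**3. Change score against adjustment.** Per arm comparison, with common SD s:
- change score: variance = 2s²(1 - r) × (2/n)
- baseline-adjusted: variance = s²(1 - r²) × (2/n)
- ratio of variances = (1 + r)/2; ratio of SEs = sqrt((1 + r)/2)

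Power after adjustment is Φ(3.301/ratio - 1.960). At r = 0.5 this is Φ(3.811 - 1.960) = 0.968. The last column is 40(1 + r)/2.

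| assumed r | SE ratio | SE smaller by | 91% becomes | per arm for the same precision |
|---|---|---|---|---|
| 0.3 | 0.806 | 19% | 98.4% | 26 |
| 0.5 | 0.866 | 13% | 96.8% | 30 |
| 0.7 | 0.922 | 8% | 94.7% | 34 |
| 0.8 | 0.949 | 5% | 93.6% | 36 |
| 0.9 | 0.975 | 2.5% | 92.3% | 38 |

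A 4,000-replicate simulation at 40 per arm gave SE ratios of 0.807, 0.876, 0.936 and 0.951 at r = 0.3, 0.5, 0.7 and 0.8. For the U minus P contrast they were 0.819, 0.881, 0.933 and 0.950. For the three-way test, r is the correlation of the U minus P difference across visits, which may differ from that of U alone.

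**4. Why the table is not the gain over the written model.** The written model has four scores per participant (U and P at two visits), one random intercept and one residual. Assume unit variances, correlation r across visits, w across conditions, and rw for both. The pooled residual variance is then 1 - (r + w + rw)/3. Dividing the SE that the model reports by the change-score SE gives:
- three-way term: sqrt{[1 - (r + w + rw)/3] / [(1 - r)(1 - w)]}
- arm by time for U: sqrt{[1 - (r + w + rw)/3] / (1 - r)}

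At r = 0.3, w = 0.5 the residual is 0.683, so the ratios are sqrt(0.683/0.35) = 1.40 and sqrt(0.683/0.7) = 0.99. At r = 0.8, w = 0.7 the residual is 0.313, so they are sqrt(0.313/0.06) = 2.29 and sqrt(0.313/0.2) = 1.25. For arm by time averaged over conditions the divisor is (1 - r)(1 + w); at r = 0.3, w = 0.7 the ratio is sqrt(0.597/1.19) = 0.71. The reported SE can thus be well above or somewhat below the change-score SE.

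**The case against.** **The plan is not wrong.** Arm by time is a standard analysis, and under randomisation it targets the same effect as the adjusted one. This stands. A reader might infer that H1 and H2a are biased or invalid, and the documents do not support that.

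**The gain may be small.** The documents call the assay reliable without giving r. At r = 0.9 the SE falls by only 2.5% and power moves from 91% to about 92%. This also stands. Adjustment still does not lose, apart from a negligible cost in degrees of freedom.

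**The stated power is already high.** A reader might infer that 91% is wrong or that the trial is underpowered. Neither follows, since the figure fits an effect of about 0.74 SD of change.

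**The comparison is with a change-score test, not the written model.** Correct. A reader might take the 19 to 2.5% as the improvement over the planned analysis, but step 4 of the working shows that the single random intercept gives a different SE, so the covariance structure has to be settled too.

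**Baseline is measured after randomisation.** Sections 5.0 and 6.0 randomise after the Screening Session and before Lab Visit 1. Zero expected imbalance therefore rests on blinding as well as on randomisation. The visit precedes the first dose and assignment is double-blind, so adjustment remains sound, but the condition should be stated.

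**The no-shock correction or H2b already covers it.** Neither does. Correcting for the N condition removes general startle level, not pre-treatment threat reactivity. H2b tests moderation, and it adds baseline as a predictor to a model that already has it as an outcome.

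**Conclusion.** The point holds as a loss of efficiency. As written, H1 and H2a estimate a difference in change and leave unused the precision available from a baseline that will already have been collected. Relative to a change-score comparison, the SE could be 19% smaller at r = 0.3 and 2.5% smaller at r = 0.9. If 91% is the change-score power, it would be about 98% and 92% at those two values.

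This rests on equal visit variances, two-sided 0.05, complete data at 40 per arm, and an r that the documents do not give. The direction is secure; the size is not. The gain over the model as literally specified cannot be stated until its covariance structure is.

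**What to change.** Amend section 12.0 for H1 and H2a in one of two ways, before unblinding:

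- Model the follow-up U and P scores (acute visit for H1, post-treatment visit for H2a) on arm, condition and arm by condition, with the matching baseline scores as covariates, each by condition.
- Preferably, where visits are missing, fit a mixed model with baseline means constrained to be equal across arms and an unstructured within-participant covariance over visit and condition. It keeps participants who have only some visits, whereas covariate adjustment drops anyone without both. The two are not interchangeable when data are incomplete.

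Three points go with this:

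- **Outcome.** Use the single startle score that the plan settles on. Section 6.0 names both standardized residual scores and condition means, section 9.0 subtracts the N condition, and section 12.0 refers to magnitude. These must be reconciled first.
- **Tests.** Keep arm by condition as the test of specificity. Any separate test of the arm effect on U should be counted under the Bonferroni rule in section 10.0.
- **H2b.** Respecify it so that baseline startle is not both an outcome and a predictor in one model.

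The cost is analysis wording only, with no new data, visits or participants.

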EMG/EEG Lab Visits. Task 1: Startle response to threat. Consistent with prior studies^{54,55}, participants will first complete a brief habituation task to prevent early exaggerated startle responding, during which a series of acoustic startle probes will be administered. For the threat task itself, a brief, mild electric shock will be used to elicit aversive responding. Importantly, the current shock equipment and shock protocol has previously been used in our laboratory. Prior to the task, shock electrodes will be placed on the participants' left wrist, followed by a shock work-up procedure in which they will receive increasing levels of shock intensity (max. = 5 mA) until they reach a level that they describe as feeling "highly annoying but not painful." Shock level will be determined ideographically to ensure equality in perceived shock aversiveness. The task itself includes three within-subjects conditions – no shock (N), predictable shock (P), and unpredictable shock (U). Text at the bottom of the screen informs participants of the current condition. Conditions last 145-s, during which a 4-s visual countdown (CD) is presented six times. The interstimulus intervals (ISIs) range from 15 to 21-s during which only the text of the condition is on the screen. No shocks are delivered during the N condition. A shock is delivered every time the CD reaches 1 during the P condition. Shocks are delivered at random during the U condition. Startle probes are administered during both the CD and ISI. Each condition is presented two times in a randomized order. Participants receive 24 shocks (12 in P; 12 in U) and 60 startle probes (20/condition). This task will be conducted during all three EMG visits, including the Acute Drug Challenge Visit.

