Startle Data Collection and Processing. Via Presentation software (Albany, CA), acoustic startle probes that are 40-ms duration, 103-dB bursts of white noise will be presented. Electric shocks will last 400-ms. Startle will be recorded using the PI's BioSemi Active Two system (BioSemi, Amsterdam, The Netherlands) and data collected and processed (e.g., filtering, rectification, smoothing, scoring blinks) according to published guidelines, as reported in the PI's publications⁵⁶⁻⁵⁸. Startle is processed using the PI's interactive 'batch' program in BrainVision Analyzer 2 (Brain Products). Consistent with the PI's work, and published recommendations⁵⁹, we will calculate standardized residual scores for the two forms of threat anticipation - U-threat and P-threat. This method has been shown to most accurately quantify the difference between threat and no-threat reactivity. Blinks will be scored as missing if the baseline period was contaminated with noise, movement artifact, or if a spontaneous or voluntary blink began before minimal onset latency. For each task, mean blink magnitude scores for each condition (N, P, U) will be calculated and used in primary analyses.

EMG/EEG Visits. Task 2: Alcohol Cue Reactivity. Participants will complete a modified Alcohol Cue Reactivity Task⁷¹. The task consists of four conditions: alcoholic

Condition	CD	ISI	CD	ISI
No-Shock (N)	321 No Shock	321 No Shock	321 No Shock	321 No Shock
Predictable Shock (P)	321⚡ Shock at 1	321⚡ Shock at 1	321⚡ Shock at 1	321⚡ Shock at 1
Unpredictable Shock (U)	321⚡ Shock Anytime	321⚡ Shock Anytime	321⚡ Shock Anytime	321⚡ Shock Anytime

beverages, non-alcoholic beverages, pixilated control images, and fixation (rest) periods. Each of the 4 conditions consists of 22 stimuli each presented four times. Stimuli are presented sequentially in a pseudo-randomized order each for about 1 second with a 1250 ms inter-stimulus interval. Alcohol and non-alcohol beverage stimuli were previously standardized to ascertain adequate identification, and comparable valence, arousal, and visual characteristics between the two conditions⁷¹. Throughout the task, participants will be instructed to indicate their mood and the valence of the different stimuli.

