9.0 Data Analysis

- Startle Data Collection, Processing and Statistical Analysis: Stimuli will be administered using Presentation software (Albany, CA) and data collected using

Biosemi Actiview 2 system. Acoustic startle probes will be 40-ms duration, 103-dB bursts of white noise with near-instantaneous rise time presented binaurally through headphones. For the threat task, electric shocks will last 400-ms. Startle responses will be recorded and data collected and processed (e.g., filtering, rectification, smoothing, scoring blinks) according to published guidelines. The startle data will be processed using an interactive 'batch' program that the PI developed in BrainVision Analyzer (BrainProducts). The PI's data indicate that ~7% of blinks are "missing" and thus, we will administer a large number of startle probes (72) to ensure that missing responses do not bias analyses. Consistent with prior studies, we will create startle potentiation scores for U and P, which account for individual differences in baseline reactivity by subtracting responses during the N condition. All variables will be checked for inter- and intra-measure consistency, and frequency distributions will be examined for outliers. Data transformations will be employed as necessary.

- EEG Data Collection, Processing and Statistical Analysis: During the Alcohol Cue Reactivity task we will record continuous electroencephalography (EEG) readings using a 32 channel ActiveTwo BioSemi system (BioSemi, Amsterdam, Netherlands). The data is recorded off the scalp, non-invasively, while participants are wearing a stretch lycra EEG cap. The EEG signal will be pre-amplified at the electrode to improve the signal-to-noise ratio. The data will be digitized at 24-bit resolution with a Least Significant Bit (LSB) value of 31.25nV and a sampling rate of 1024Hz, using a low-pass fifth order sinc filter with a -3dB cutoff point at 204.8Hz. Off-line analysis will be performed using Brain Vision Analyzer software (Brain Products), using conventional preprocessing steps. Data will be re-referenced to the average of the two mastoids and high-pass (0.1Hz) and low-pass (30Hz) filtered. Data will be segmented around event markers that correspond to the administration of task stimuli. Baseline correction for each trial will be performed and brain activity averages will be computed for each condition, for each task.

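### Fitted with only a participant random effect, the H1/H2a model makes the U-specific three-way test conservative and costs power; an arm × session test from the same model can be mis-sized in either direction

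*Combined protocol and SAP*

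**What the plan says.** Section 12.0, under Aim 1, sets out a multilevel mixed model for startle with time (baseline, acute challenge) within participants and arm between participants. Condition is the second within-participant factor: "Startle to U-threat and P-threat will be included as a within-subjects factor, to test for specific changes in U-threat". The effect to be tested is named: "we expect a time x treatment arm x task condition interaction on startle". On the random part it says only "Models will include a random effect for participant". For H2a, "we will conduct a multilevel mixed model that is nearly identical to the model described for H1", with post-treatment in place of the acute challenge.

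The sample-size paragraph at the end of the same section refers to a different, two-way test: "Our key hypothesis testing involves treatment arm by session interactions on startle eyeblink potentiation". It gives 91% power at 40 per arm.

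Section 6.0 (Startle Data Collection and Processing) says that condition means go into the primary analyses, so each participant contributes four values to each model. The score is described in three ways. Section 12.0 calls it startle magnitude. Section 6.0 says "we will calculate standardized residual scores for the two forms of threat anticipation". Section 9.0 adjusts for "baseline reactivity by subtracting responses during the N condition". No section names a participant-by-visit term, a participant-by-condition term or a residual covariance structure.

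**The concern.** A single participant intercept assumes that, apart from a participant's overall level, the four values are independent with equal variance. Two features of this trial make that unlikely. Startle can shift as a whole from one visit to the next. The trial's premise is also that people differ stably in their response to U-threat as distinct from P-threat. When either source of variance exists, the different within-participant contrasts have different true errors, but the fitted model gives them all the same one.

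The three-way interaction is the test of a change in U-threat but not P-threat, which is the central mechanistic claim of H1 and H2a. A needlessly wide standard error there could miss a real U-specific effect in a study meant to inform and power a larger trial. If the arm × session test is taken from the same model, its error rate is not controlled at the nominal level.

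**Working it through.** **The plan's own figure.** The 91% cannot be uniquely reproduced, because alpha, sidedness, a numerical effect size and a correlation are not given. Assuming two-sided 5% and 40 per arm, power ≈ Φ(d√(40/2) − 1.96). This is 61% at d = 0.5, 91% at d = 0.74 and 95% at d = 0.8. The stated figure is plausible for an effect between medium and large. With the t distribution on 78 df, 91% needs d ≈ 0.75 on the change-score SD. That value is used below for the three-way test; this is an assumption, since the plan claims 91% only for arm × session.

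**Error terms.** Let e be the residual variance, pv the participant-by-visit variance and pc the participant-by-condition variance. Form three orthonormal contrasts per participant. Their true mean squares are:

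- session (gives arm × session averaged over U and P): e + 2pv
- condition: e + 2pc
- session × condition (gives the three-way test): e

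The random-intercept model replaces all three with their mean, on 3 × 78 = 234 df:

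(3e + 2pv + 2pc)/3 = e + (2/3)(pv + pc).

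Hence:

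- Three-way: fitted SE / true SE = √[1 + (2/3)(pv + pc)/e]. With non-negative components this is never below 1, and it exceeds 1 whenever pv or pc is above 0.
- Averaged arm × session: the fitted SE is too small when e + 2pv > e + (2/3)(pv + pc), that is when pv > pc/2. It is right at equality and too large below that.

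**Illustrative sizes.** 40 per arm, e = 1, 8,000 to 20,000 simulated trials per row:

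| pv, pc | Pooled error | Three-way SE ratio | Three-way type I | Three-way power | Averaged arm × session type I |
|---|---|---|---|---|---|
| 0, 0 | 1.00 | 1.00 | 5.3% | 92% | 5.0% |
| 0.5, 0 | 1.33 | 1.15 | 2.5% | 86% | 11.0% |
| 1, 0 | 1.67 | 1.29 | 1.2% | 78% | 14.6% |
| 0, 1 | 1.67 | 1.29 | 1.2% | 79% | 1.2% |
| 0.5, 0.5 | 1.67 | 1.29 | 1.1% | 78% | 7.0% |
| 0.25, 1 | 1.83 | 1.35 | 0.8% | 76% | 3.2% |
| 0.5, 1 | 2.00 | 1.41 | 0.5% | 71% | 5.2% |
| 1, 1 | 2.33 | 1.53 | 0.3% | 63% | 8.5% |

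With the correct error term, the three-way test stayed near 5% type I error and 91% power throughout. A U-only contrast taken from the joint model ran between 1.3% and 7.4%; a model fitted to U alone ran at 5.0%.

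The pooled-error calculation agrees with actual REML fits of the single-intercept model (t statistics within 1e-5 in 20 datasets). In one further simulated dataset with pv = 1 and pc = 0.5, the fitted three-way SE was 0.643 against 0.504 from the contrast itself. For arm × session it was 0.321 against 0.388.

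**Sample size to regain 91%.** n per arm = 40 × [(1.96√(pooled/e) + 1.34)/(1.96 + 1.34)]². At (0.5, 0) this is 40 × (3.60/3.30)² ≈ 48; at (1, 0), 40 × (3.87/3.30)² ≈ 55; at (1, 1), 40 × (4.33/3.30)² ≈ 69.

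**Effect of the score.** Subtracting the same N mean from U and P at a visit puts N's measurement error into both scores, which adds that error variance to pv. Section 6.0 gives N as many probes as U and P (20 each), so equal error is a reasonable case. Then pv = 1 and pc = 0 even with no true visit variation, which is the third row of the table. Simulated three-way / averaged arm × session type I error, 10,000 trials each:

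| Score | No true visit or condition variance, equal N error | Both variances 0.5, N error half that of U and P |
|---|---|---|
| N subtracted | 1.3% / 14.4% | 1.2% / 7.3% |
| Standardised residual on N | 2.1% / 11.9% | 1.5% / 6.0% |
| Raw magnitude | 5.1% / 5.1% | 1.1% / 7.1% |

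**The case against.** The strongest reply is that the plan says a participant effect will be included, not that it is the only one, so the fault is an unstated covariance. That is fair as far as it goes. But no other term appears anywhere, and an analyst following the text would fit the single-intercept model.

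Several limits stand:

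- The size of the loss rests on variance components that the documents do not give. If both are zero, nothing is lost.
- The 91% anchor for the three-way test is borrowed from the arm × session claim.
- The scoring argument does not apply to raw magnitude, which Section 12.0 names and Section 6.0 also supports. Subtracting N can also remove visit-state variance common to N, U and P, so it may lower pv as well as raise it. Once real visit and condition variance is present, the choice of score makes little difference.
- The sample-size paragraph does not say that arm × session is averaged over U and P, and an average would not test the hypothesis. If U is analysed alone, with two values per participant, the problem does not arise.
- For the three-way test the consequence is lost power, not false positives.

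None of this alters the direction of the three-way result. Zero for both components is the special case, and it sits badly with a trial built on stable individual differences in U-threat reactivity.

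**Conclusion.** The concern holds and should be fixed. Fitted as written to condition means, the H1 and H2a models give the three-way test a standard error inflated by √[1 + (2/3)(pv + pc)/e]. The algebra and direction are firm given non-negative components. The size is illustrative: with components between half and all of the residual variance, a 91% test becomes roughly 86% to 63%. The arm × session test is affected only if it is read from this joint model, and then in a direction that depends on whether pv exceeds pc/2 (averaged over U and P) or pv exceeds 2pc (U alone).

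The conclusion assumes two-sided 5%, one value per participant, visit and condition, complete data, and no further random or residual structure. If single blinks were modelled instead of means, a lone participant effect could make the three-way standard error too small.

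**What to change.** Write the covariance for H1 and H2a into the SAP. One option is an unstructured covariance over the four visit-by-condition values within participant. The other is to add participant-by-visit and participant-by-condition random effects to the participant effect. Use Kenward-Roger degrees of freedom in either case. This alone restores about 5% type I error and, under the assumed effect, about 91% power for the three-way test.

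As a gain in precision beyond the repair, use the baseline startle already collected by constraining baseline means to be equal across arms, or by adjusting for baseline. For the three-way test this multiplies the variance by (1 + ρ)/2, where ρ = pc/(e + pc) is the between-visit correlation of the U-minus-P difference. With e = 1, the factor is 0.50 at pc = 0 and 0.75 at pc = 1, taking 91% power to 99.7% and 96.8%. The second is the more relevant case if U-specific differences are stable. Terms for sex and for protocol arm × time may be added for precision, but leaving them out does not cause this error.

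The cost is SAP wording. An unstructured 4 × 4 covariance has 4 × 5/2 = 10 parameters, which 80 participants can support. No new data or visits are needed. Settling it before unblinding also avoids a post hoc choice of error term.
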